7.3 LOST TO FOLLOW-UP

A participant will be considered lost to follow-up if she fails to return for 2 scheduled intervention sessions, or 1 data collection session and study staff are unable to contact the participant after at least 3 attempts.

The following actions must be taken if a participant fails to attend a data collection visit or intervention session (unless there is a documented reason why they were absent):

- The study team will attempt to contact the participant, reschedule the missed visit, counsel the participant on the importance of maintaining the assigned visit schedule and ascertain if the participant wishes to and/or should continue in the study
- Before a participant is deemed lost to follow-up, the investigator or designee will make every effort to regain contact with the participant (where possible, 3 telephone calls and, if necessary, a certified letter to the participant's last known mailing address or local equivalent methods). These contact attempts will be documented in the participant's study file.
- Should the participant continue to be unreachable, she will be considered to have withdrawn from the study with a primary reason of lost to follow-up.

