Study 4: 68 AA adults were enrolled to compare a mindfulness-based pre-diabetes (MPD) prevention program to a conventional diabetes prevention program for AA adults (>80% AAW) with pre-diabetes (Grant # R21 AT004276-03),^{76,51} using a mixed-methods, two-arm RCT. Participants reported acceptability, credibility, and cultural-relevance of the intervention. Enrollment of eligible participants (79%), session attendance (76.5%), retention (90%), and attendance at three post-intervention data collection sessions (83%, 82%, and 78%, respectively) demonstrated feasibility. MPD resulted in reductions in perceived stress and BMI, reduced calorie, fat, and carbohydrate intake, and improved quality of life. Both groups reported increased knowledge about strategies to improve diet and exercise. MDP participants reported using mindfulness, breathing techniques, and conscious eating behaviors, and were more aware of stress. Participants recommended improvements that form the basis for this proposal: 1) explicit discussion of the potential impact of culturally-relevant, contextualized stressors for AAW; 2) incorporation of strategies in the mindfulness sessions for overcoming guilt and resistance to self-sacrifice by enhancing self-compassion; and 3) incorporating strategies to help AAW overcome physical and psychological barriers to home-based mindfulness practice, exercise, and healthy eating (e.g., accountability partners).

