9.2 SAMPLE SIZE DETERMINATION

200 participants will be enrolled (100 each in HARMONY and NEEW). Conservatively, based on prior research, comparisons of complete data on 80 participants per group are assumed, and also assume 20% attrition. Power calculations were performed with POWERLIB20 SAS/IML modules that incorporate methods to calculate power for the general linear multivariate model, which includes repeated measures data structures. Based on pilot study data, power analysis focuses on a group of representative variables addressed in the primary and secondary endpoints for CM risk factors. For primary and secondary endpoints, power is based on a separate multivariate model for these outcomes, incorporating measures from all timepoints. It is hypothesized that through improvements in self-management, women in HARMONY (experimental group) will show greater sustained improvements in exercise and healthy eating behaviors (primary endpoint) and greater reduction of CM risk biomarkers (secondary endpoint). Each hypothesis will be considered by specifying both a between-group contrast (HARMONY vs. NEEW) and the appropriate within-group contrast (three post-baseline timepoints versus baseline). This facilitates testing the null hypothesis that both groups have the same difference in population means for the change from baseline at a specific post-baseline time point against the alternative that the between-group difference of the change from baseline significantly differs from 0.

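### Sections 7.2 and 7.3 let poor attendance end outcome collection: one unsuccessful round of contact after missed sessions or one missed visit counts as study withdrawal, and no later approach at week 32 or 48 is required

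*Combined protocol and SAP*

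**What the plan says.** Section 7.3 defines the status: "A participant will be considered lost to follow-up if she fails to return for 2 scheduled intervention sessions, or 1 data collection session". A second condition follows in the same sentence: "and study staff are unable to contact the participant after at least 3 attempts". After an absence without a documented reason, "The study team will attempt to contact the participant, reschedule the missed visit, counsel the participant" and establish whether she wishes to, or should, remain in the study. The label comes only after further effort: "Before a participant is deemed lost to follow-up, the investigator or designee will make every effort to regain contact with the participant", by three telephone calls where possible and a certified letter if necessary. The consequence is exit from the study: "Should the participant continue to be unreachable, she will be considered to have withdrawn from the study with a primary reason of lost to follow-up".

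Three other sections bear on this.

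- Section 7.1: a woman who stops the sessions but not the study completes the remaining study procedures.
- Section 7.2: the investigator may discontinue a woman from the study for several reasons. One is loss to follow-up, described there as inability to contact her. Another is significant non-compliance with the intervention, which is not defined and does not depend on failed contact.
- Section 9.3: the analysis is by intention to treat, according to random assignment.

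The primary endpoints in section 3 are changes from baseline to 48 weeks after the first group session. On sample size, section 9.2 says "comparisons of complete data on 80 participants per group are assumed, and also assume 20% attrition".

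**The concern.** Attendance at sessions measures adherence. Availability for outcome measurement is a different matter, and an intention-to-treat comparison needs the outcome whether or not a woman attended. Section 7.3 makes missed sessions, or a single missed interim data visit, the first step towards study withdrawal. The second step is one unsuccessful round of contact, made when the absences occur. Being unreachable in the second month does not establish that she is unreachable in the twelfth, yet no section calls for another attempt at week 32 or week 48.

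Section 7.2 exposes women who can be reached. Poor attendance can be judged significant non-compliance and lead to discontinuation from the study, and nothing says that outcomes are then still collected. This weakens the protection that section 7.1 gives.

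At stake is selective loss of the primary outcome among poor attenders. Analysis by assigned arm cannot recover outcomes that were not collected. The model in section 9.4.1 is described as fitted to the outcome at the three follow-up times with the baseline value as a covariate, so a woman closed out before week 16 would contribute no outcome to it. Section 9.4 plans no sensitivity analysis for missing data.

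**Working it through.** **The plan's own figure.** Section 9.2 assumes 80 completers per group and 20% attrition: 80 / (1 − 0.20) = 100 per group, 200 in total. This reproduces the stated enrolment exactly. The allowance to compare against is therefore 20%.

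**Timing.** Section 4.1 places the eight core sessions at weeks 1, 3, 5, 7, 9, 11, 13 and 15. A woman who attends session 1 and misses sessions 2 and 3 meets the attendance part of the trigger at week 5, more than 40 weeks before the primary assessment.

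**Exposure to the missed-session trigger.** Inputs: pilot session attendance of 76.5% (section 2.2, Study 4), so a miss probability of q = 0.235; 8 core and 6 booster sessions (section 4.1). Independence of misses is an assumption.

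P(at least 2 missed of k) = 1 − 0.765^k − k × 0.235 × 0.765^(k−1)

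- k = 8: 1 − 0.117 − 0.288 = 0.594, or 59%.
- k = 14: 1 − 0.024 − 0.101 = 0.875, or 88% (unrounded, 0.8754).
- At 90% attendance: 19% for k = 8 and 42% for k = 14.

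Section 7.3 does not say whether the two misses must be consecutive. If they must, let a(n) be the probability of no two consecutive misses in n sessions: a(n) = 0.765 × a(n−1) + 0.235 × 0.765 × a(n−2), with a(0) = a(1) = 1. This gives a(8) = 0.711, so exposure is 1 − 0.711 = 0.289, about 29%.

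**From exposure to loss.** Section 7.3 also needs failed contact. Loss = exposure × u, where u is the fraction who cannot be reached among those meeting the attendance part. The documents give no value for u, so a range is shown:

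| u | any 2 of 8 | any 2 of 14 | 2 in a row of 8 |
|---|---|---|---|
| 5% | 3.0% | 4.4% | 1.4% |
| 10% | 5.9% | 8.8% | 2.9% |
| 20% | 11.9% | 17.5% | 5.8% |
| 34% | 20.2% | 29.8% | 9.8% |

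The value of u at which this route alone would use up the 20% allowance is 0.20 / 0.594 = 34% for any 2 of 8, 0.20 / 0.875 = 23% for any 2 of 14, and 0.20 / 0.289 = 69% for two in a row of 8.

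**Missed data visits.** Pilot attendance at the three post-intervention data collections was 83%, 82% and 78%. If the first two stand for weeks 16 and 32, the share missing at least one lies between 18% (misses fully overlapping) and 1 − 0.83 × 0.82 = 32% (independent). A missed interim visit is an ordinary event. This too is exposure and must be multiplied by an unknown unreachable fraction.

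**What cannot be computed.** Section 9.2 gives power only for BMI, A1C and waist-hip ratio, so the cost in power for the three primary outcomes cannot be derived from the documents.

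**The case against.** The strongest objection is that section 7.3 is a contact rule and not an attendance rule. A reader who stops after the first half of the defining sentence might infer that two missed sessions alone remove a woman, so that 59% to 88% would be lost and 80 completers per arm could not be reached. The documents do not support that. The sentence goes on to require failed contact. The steps beneath it tie withdrawal to remaining unreachable, and section 7.2 describes the reason in the same way. If absence were enough, the contact steps would have no function. The order of the clauses is loose and worth tidying, but the intent is clear: a poor attender who can be reached is not withdrawn under section 7.3.

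Three further points on that side also stand.

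- Section 7.1 is not contradicted. It concerns women who leave the sessions but not the study, whereas section 7.3 concerns women who cannot be reached.
- No section discards data already collected. The issue is data that nobody is required to seek.
- The pilot reported 90% retention, and data-visit attendance of 78% to 83%, alongside 76.5% session attendance. Modest attendance can therefore coexist with follow-up near the assumed 80%. The pilot was a different programme and its follow-up rule is not given, so this does not validate section 7.3, but it prevents any claim that the rule is incompatible with 20% attrition.

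The objection leaves two things unanswered: no further approach is required after the first unsuccessful round of contact, and the non-compliance item in section 7.2 needs no failed contact at all.

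**Conclusion.** The point holds as a defect in the follow-up rules. Missed sessions or one missed interim visit, followed by one failed round of contact, count as withdrawal from the study, possibly within the first weeks, with no required attempt at week 32 or 48. Section 7.2 adds a second route through undefined non-compliance. Both allow week-48 missingness to depend on adherence in a trial that promises intention to treat.

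The size is uncertain. Exposure to the missed-session trigger is 59% over 8 sessions and 88% over 14 at pilot attendance, or about 29% over 8 if two in a row are meant. Loss is that exposure times an unknown unreachable fraction: over 8 sessions, about 6% at 10% unreachable and about 20% at 34%. These figures rest on independent misses and on attendance carried over from a different programme; clustering of misses would lower the figures for any two misses. Some of these women would have missed week 48 under any rule, so the avoidable part is smaller. The number affected through section 7.2 cannot be estimated.

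A reader might also infer a bias in favour of one arm. The documents do not show one: they give no attendance by arm, and the direction of any bias is unknown.

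**What to change.** Amend section 7.3 to state that:

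- failed contact is required under both triggers;
- missed sessions are recorded as non-adherence only;
- a missed week-16 or week-32 assessment is a missed visit, after which contact is attempted again at each later assessment, including week 48, for every randomized woman who has not withdrawn consent;
- final lost-to-follow-up status is assigned only after the week-48 attempts have failed.

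Amend section 7.2 to state that non-compliance with the intervention does not in itself end outcome collection. The other reasons listed there need not change.

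The cost is a short amendment and some extra contact attempts by existing staff around weeks 32 and 48. Sample size, visit schedule and primary model are unaffected.

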8 STUDY ASSESSMENTS AND PROCEDURES

8.1 ENDPOINT AND OTHER ASSESSMENTS

The procedures and assessments described in this section will be performed at the time points described in the schedule of activities in section 1.3.

Endpoint Assessments

Superwoman Schema Questionnaire

The participant's endorsement of Superwoman Schema will be measured using the [name] Superwoman Schema Questionnaire, which includes 35 items, divided in 5 subscales, on a 4-point scale, ranging from 0 to 3. The [name] Superwoman Schema Questionnaire measures obligation to present an image of strength, obligation to suppress emotions, resistance to vulnerability, intense motivation to succeed, obligation to help others. There are 5 different subscales for the superwoman schema, so participants will report 5 different scores. Score ranges for each subscale are 0-18 (strength), 0-21 (suppress emotions), 0-21 (resistance to vulnerability), 0-18 (motivation to succeed), 0-27 (obligation to help others), with higher scores associated with a greater endorsement of the selected superwoman schema scale characteristic.

This questionnaire will be performed at telephone screening and 16, 32, and 48 weeks post first group session. The data will be entered electronically by the patient through REDCap survey; however, paper copies of the questionnaire may be used if necessary.

Perceived Stress Scale

The participant's general stress will be measured using the PSS-14, which includes 14 items on a 5-point scale. Scores range 0-56, with higher scores indicating greater perceived stress.

This questionnaire will be performed at telephone screening and 16, 32, and 48 weeks post first group session. The data will be entered electronically by the patient through REDCap survey; however, paper copies of the questionnaire may be used if necessary.

Actigraphy

Participants will be given a triaxial ActiGraph Activity Monitor at baseline and 16, 32, and 48 weeks post first group session. Participants will be instructed to wear the ActiGraph Activity Monitor for 7 consecutive days. Participants will be instructed how to wear the ActiGraph Activity Monitor and special instructions for care by study personnel.

For the purposes of this study, the participant's moderate to vigorous physical activity will be measured. Moderate to vigorous physical activity is defined as activities that are strenuous enough to burn off three to six times as much energy per minutes as one does when sitting quietly, or exercises that clock in at 3 to 6 METs.

Dietary Risk Assessment

The participant's dietary intake will be assessed using the dietary risk assessment, which includes 54 items. The dietary risk assessment measures the healthiness of a participant's eating habits. Score ranges from 0 to 108, with higher scores associated with less healthy dietary intake.

This questionnaire will be performed at baseline and 16, 32, and 48 weeks post first group session. The data will be entered electronically by the patient through REDCap survey; however, paper copies of the questionnaire may be used if necessary.

Veggie Meter

The participant's fruit and vegetable intake will be measured by the participant's skin carotenoids. The Veggie Meter uses a pressure-mediated reflection spectroscopy device to measure these carotenoids. Study personnel will calibrate the Veggie Meter as needed, and then ask the participant to wash their hands with soap and water. The participant will then place their finger in the cradle of the meter, and will hold it there until the scan is complete.

The Veggie Meter procedure will be performed at baseline and 16, 32, and 48 weeks post first group session.

Weight and Height

The participant's weight will be measured using an electronic scale. Weight will be converted to kilograms to calculate participant BMI. The participant's height will be measured to the nearest centimeter to calculate participant BMI.

Weight will be performed at baseline and 16, 32, and 48 weeks post first group session. Height will be performed at baseline, and is optional to perform at 16, 32, and 48 weeks post first group session.

Hip Circumference

Hip circumference will be measured at the maximum width of the buttocks or gluteo-femoral fold. Two measurements will be recorded by study personnel. The mean of these measurements will be used for the waist-to-hip ratio.

Hip circumference will be measured at baseline and 16, 32, and 48 weeks post first group session.

Waist Circumference

Waist circumference will be measured at the midpoint between the upper iliac crest and lower costal margin in the midaxillary line. Study personnel will record two waist circumference measurements. The mean of these measurements will be used for the waist-to-hip ratio.

Waist circumference will be measured at baseline and 16, 32, and 48 weeks post first group session.

IL-6 and CRP

Specimens for the measurement of IL-6 and CRP will be collected using standard venipuncture.

The phlebotomy procedure to obtain the IL-6 and CRP measurements will be completed at baseline and 16, 32, and 48 weeks post first group session.

HgbA1C

HgbA1C will be assessed using a fingerstick procedure at baseline and 16, 32, and 48 weeks post first group session.

Blood Pressure

Blood pressure will be collected by an electronic sphygmomanometer after a five-minute rest in the sitting position. Study personnel will record three blood pressure measurements, and the average value will be used for analysis.

Blood pressure will be measured at baseline and 16, 32, and 48 weeks post first group session.

Contextualized Stress Scale

The participant's racial and gendered stress exposure will be measured using the Contextualized Stress Measure, which includes 69 items on a 5-point scale. The Contextualized Stress Measure is divided into six subscales, including race/racism, burden, personal history, workplace, coping and support, and stress states. Score ranges from 0 to 345, with higher scores associated with increased stress exposure.

This questionnaire will be performed at baseline and 16, 32, and 48 weeks post first group session. The data will be entered electronically by the patient through REDCap survey; however, paper copies of the questionnaire may be used if necessary.

Network Stress Scale

The participant's indirect and self-stress will be measured using the Network Stress Scale, which includes 10 items on a 4-point scale. The Network Stress scale assesses both exposure and appraisal of events that happened to both self and close family members and friends. Higher scores represent higher exposure and appraisal. Score ranges from 0, with 10 scores associated with a higher amount of indirect and self-stress.

This questionnaire will be performed during the pre-baseline period and 16, 32, and 48 weeks post first group session. The data will be entered electronically by the patient through REDCap survey; however, paper copies of the questionnaire may be used if necessary.

Mindful Eating Questionnaire

The participant's mindful eating will be measured using the Mindful Eating Questionnaire, which includes 28 items on a 4-point scale. Score ranges from 1 to 4, with higher scores associated with more mindful eating.

This questionnaire will be performed during the pre-baseline period and 16, 32, and 48 weeks post first group session. The data will be entered electronically by the patient through REDCap survey; however, paper copies of the questionnaire may be used if necessary.

Mindful Self-Care Scale

The participant's self-care will be measured using the Mindful Self-Care scale, which includes 42 items on a 5-point scale. The Mindful Self-Care scale assesses 6 domains of self-care: physical care, supportive relationships, mindful awareness, self-compassion and purpose, mindful relaxation, and supportive structure. Score ranges from 1 to 5, with higher scores higher associated with more self-care.

This questionnaire will be performed at baseline and 16, 32, and 48 weeks post first group session. The data will be entered electronically by the patient through REDCap survey; however, paper copies of the questionnaire may be used if necessary.

Cognitive Emotion Regulation Questionnaire

The participant's cognitive emotion regulation strategies will be measured using the Cognitive Emotion Regulation questionnaire, which includes 20 items on a 5-point scale. The Cognitive Emotion Regulation Questionnaire assesses the sub-scales of self-blame, other-blame, rumination, catastrophizing, positive refocusing, planning, positive reappraisal, putting into perspective and acceptance. Scores for each sub-scale ranges from 2 to 10, with higher scores associated with an increased usage of a specific cognitive strategy.

This questionnaire will be performed during the pre-baseline period and 16, 32, and 48 weeks post first group session. The data will be entered electronically by the patient through REDCap survey; however, paper copies of the questionnaire may be used if necessary.

PROMIS Self-Efficacy for Managing Emotions

The participant's management of emotions will be measured using the PROMIS Self-Efficacy for Managing Emotions, which includes 4 items on a 5-point scale. The PROMIS Self-Efficacy for Managing Emotions assesses the participant's confidence to manage and control symptoms stress, discouragement, disappointment, and negative feelings. Score ranges from 5 to 20, with higher scores associated with a higher confidence level in managing symptoms.

This questionnaire will be performed during the pre-baseline period and 16, 32, and 48 weeks post first group session. The data will be entered electronically by the patient through REDCap survey; however, paper copies of the questionnaire may be used if necessary.

PROMIS Emotional Distress-Depression Scale

The participant's depressive symptoms will be assessed using the PROMIS Emotional Distress- Depression Scale, which includes 4 items on a 5-point scale. The PROMIS Emotional Distress-Depression Scale assesses self-reported negative mood, views of self, social cognition, and decreased positive affect and engagement. Scores range from 5 to 20, with higher scores associated with a higher degree of depressive symptoms.

This questionnaire will be performed during the pre-baseline period and 16, 32, and 48 weeks post first group session. The data will be entered electronically by the patient through REDCap survey; however, paper copies of the questionnaire may be used if necessary.

Connor-Davidson Resilience Scale

The participant's resilience will be measured using the Connor-Davidson Resilience Scale, which includes 10 items on a 4-point scale. The Connor-Davidson Resilience Scale assesses ability to adapt to change, achievement of goals despite obstacles, and how participants handle strong feelings. Score ranges from 0 to 40, with higher scores associated with increased resiliency.

This questionnaire will be performed during the pre-baseline period and 16, 32, and 48 weeks post first group session. The data will be entered electronically by the patient through REDCap survey; however, paper copies of the questionnaire may be used if necessary.

Self-Efficacy for Exercise Scale

The participant's perceived self-efficacy for healthy exercise will be measured using the Self-Efficacy for Exercise Scale, which includes 9 items on a 11-point scale. Scores range from 0 to 90, with higher scores associated with higher self-efficacy for exercise.

This questionnaire will be performed at baseline and 16, 32, and 48 weeks post first group session. The data will be entered electronically by the patient through REDCap survey; however, paper copies of the questionnaire may be used if necessary.

Diet Self Efficacy Scale

The participant's perceived self-efficacy for healthy eating will be measured using the Diet Self-Efficacy scale, which includes 11 items on a 5-point scale. The Diet Self Efficacy Scale assesses high caloric food temptations, social and internal factors, and negative emotional events which impact eating behaviors. Scores range from 0 to 44, with higher perceived self-efficacy for healthy eating.

This questionnaire will be performed at baseline and 16, 32, and 48 weeks post first group session. The data will be entered electronically by the patient through REDCap survey; however, paper copies of the questionnaire may be used if necessary.

Five Facet Mindfulness Scale

The participant's level of mindfulness will be measured using the Five Facet Mindfulness Scale, which includes 39 items on a 5-point scale. The Five Facet Mindfulness Scale measures observing, the ability to verbally express one's experience, acting with awareness, nonjudging of inner experience, and non-reacting to one's inner experience. Score ranges from 1-5, with higher scores associated with a higher level of mindfulness.

This questionnaire will be performed at baseline and 16, 32, and 48 weeks post first group session. The data will be entered electronically by the patient through REDCap survey; however, paper copies of the questionnaire may be used if necessary.

Other Assessments**Cardiometabolic Risk Questionnaire**

The cardiometabolic risk questionnaire will be performed during the screening period to assess for BMI, exercise frequency, family history, and cardiometabolic medical history.

The data will be entered electronically by the patient through REDCap survey; however, paper copies of the questionnaire may be used if necessary.

Physical Activity Readiness Questionnaire

The physical activity readiness questionnaire will be performed during the screening period to assess if the participant is able to exercise.

The data will be entered electronically by the patient through REDCap survey; however, paper copies of the questionnaire may be used if necessary.

Demographics Questionnaire

The demographics questionnaire will be administered during the screening period to collect information regarding the participant's age, race, socioeconomic class, and other elements.

The data will be entered electronically by the patient through REDCap survey; however, paper copies of the questionnaire may be used if necessary.

Health History Questionnaire

The health history questionnaire will be administered during the screening period to obtain information about the participant's medical history and medication usage.

The data will be entered electronically by the patient through REDCap survey; however, paper copies of the questionnaire may be used if necessary.

University of Rhode Island Change Assessment Scale

The University of Rhode Island Change Assessment Scale assesses the participant's readiness for change. Scores range from +2 to +14.

This questionnaire will be performed during the first group session and at the half-day retreat. The data will be entered electronically by the patient through REDCap survey; however, paper copies of the questionnaire may be used if necessary.

Fitbit Measurements

Fitbit devices will be provided to each participant at the baseline visit. The participant will be instructed to wear the Fitbit consistently for the duration of the study.

A research staff member will create a email and password for each participant to connect the Fitbit device to the Fitabase platform.

Group Cohesion Questionnaire

The Group Cohesion Questionnaire assesses the participant's perception of group cohesion, which includes 12 items on a 7-point scale. Scores range from 12 to 84, with higher scores associated with less group cohesion.

This questionnaire will be performed at group sessions 2 and 7. The data will be entered electronically by the patient through REDCap survey; however, paper copies of the questionnaire may be used if necessary.

Credibility Scale

The credibility scale assesses the participant's expectation of benefit once the intervention has been explained to them. It includes 5 items on a 10-point scale. Scores range from 0 to 45, with higher scores associated with higher expectation on benefit.

This questionnaire will be performed at group sessions 2 and 7. The data will be entered electronically by the patient through REDCap survey; however, paper copies of the questionnaire may be used if necessary.

Buddy System Assessment

The buddy system assessment measures how often participants are communicating with their buddy, barriers to their participation in the buddy system, and other elements regarding the system.

This questionnaire will be performed at all group sessions, and at 16, 32, and 48 weeks post first group session. The data will be entered electronically by the patient through REDCap survey; however, paper copies of the questionnaire may be used if necessary.

Mindfulness Practice Assessment

The mindfulness practice survey assesses how often the participants are practicing mindfulness. This questionnaire will only be given to participants in the HARMONY group.

This questionnaire will be performed at all group sessions, and at 16, 32, and 48 weeks post first group session. The data will be entered electronically by the patient through REDCap survey; however, paper copies of the questionnaire may be used if necessary.

Nutritional Survey

The nutritional survey assess the participants knowledge of nutrition, and also asks about current eating habits.

This questionnaire will be performed prior to group session 1 and 8. The data will be entered electronically through REDCap survey; however, paper copies of the questionnaire may be used if necessary.

General Stress Assessment

The general stress assessment measures the participants overall stress levels. It is a one-question assessment, with answers ranging from 0 (no stress at all) to 3 (extreme stress).

If the participant selects answer choices 1, 2, or 3, they are eligible for the study.

Interview

All participants will have an interview conducted at the 16- and 48-week post first group session timepoint. The interview will ask about participant opinion regarding the interventions, and the HARMONY group participants will be also asked about mindfulness and superwoman schema.

